11.7.1 Adverse Events

All Adverse events will be coded using the Medical Dictionary for Regulatory Activities (MedDRA) version 21.0 or Higher. All summaries will be based on FAS population.

11.7.1.1 Overall Adverse Events

Number and percentage of subjects will be summarized by cohort for the following categories:

1. All adverse events of interest reported
2. ADVM-043 related adverse events
3. Adverse events \geq grade 3
4. Serious adverse events
5. ADVM-043 related serious adverse events
6. Fatal adverse events

Percentages will be based on FAS population.

All adverse events will be listed by subject and system organ class. Adverse events will be grouped by subject. Duration of AEs will also be included in the listing.

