6.2 Definition of an Adverse Event

An AE is any untoward medical occurrence in an enrolled subject, regardless of its causal relationship to the investigational medicinal product. Only AEs of interest should be collected and reported.

AEs of interest include the following:

- new malignancy
- new incidence or exacerbation of a pre-existing neurologic disorder
- new incidence or exacerbation of a prior rheumatologic or other autoimmune disorder
- unexpected hospitalization

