6.3 Definition of a Serious Adverse Event

An SAE is any untoward medical occurrence in an enrolled subject that results in death; is immediately life-threatening; requires inpatient hospitalization or prolongation of existing hospitalization; results in persistent or significant disability or incapacity; or is a congenital anomaly or birth defect. Only SAEs related to ADVM-043 should be collected and reported.

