6.10 Request for Autopsy in the Event of a Subject Death

In the event of a subject death while participating in the study, the Investigator should request a full autopsy to determine the precise cause of death. If possible, samples of tissues obtained at autopsy should be evaluated for the presence of the AAV genome.

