10.6 Adverse Events Flags

An AE is any untoward medical occurrence in an enrolled subject, regardless of its causal relationship to the investigational medicinal product.

Only AEs of interest will be collected and reported in the current study. AEs of interest that are continuing from the previous study will be imported for long term follow-up.

AEs of interest include:

- new malignancy
- new incidence or exacerbation of a pre-existing neurologic disorder
- new incidence or exacerbation of a prior rheumatologic or other autoimmune disorder
- unexpected hospitalization

Study Period:

All AEs will be counted once under the below period in which the AE has started.

- Previous Study: Reported from AE (External).
- Screening – Year 1: If AE start date is after screening and on or before Year 1 visit date.
- Year 1 – Year 2: If AE start date is after Year 1 and on or before Year 2 visit date.
- Year 2 – Year 3 (EOS): If AE start date is after Year 2 and on or before Year 3 visit date.

Related Adverse Events:

- AE (External): includes Possibly, Probably and Definitely Related Adverse Events
- AE: includes Definitely and Likely Related Adverse Events.

Relationship to ADVM-043 will be flagged separately.

Severity:

Subjects with the same AE of interest and different severities will be flagged for the most intense severity. i.e., If the same event has been reported twice with severity 'Grade 1 – Mild' and 'Grade 3 – Severe' then the subject will be flagged as 'Grade 3 – Severe'. AEs that are missing severity will be presented in summary tables as 'Grade 3 – Severe'.

Duration of AEs:

Duration of Adverse events (days) will be calculated as follows: (AE End date – AE Start date) + 1.

For adverse events that are ongoing at end of study, date of end of study will be considered as AE End date.

11 Statistical Analyses

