11.7 Safety Analyses

The long-term safety of ADVM-043 is to be assessed by determining the type, frequency and percentages, severity, duration, and relationship to ADVM-043 of adverse events (AEs) of interest and serious adverse events (SAEs) related to ADVM-043. All safety data will be listed and summarized by cohort using the FAS population.

Only AEs of interest will be summarized.

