11.7.1.2 Summary of Adverse Events of Interest by SOC and PT

Number and percentage of subjects will be summarized by cohort, system organ class and preferred terms. Percentages will be based on FAS population. Events will be displayed in the descending order of frequency in “Total”.

The same will be repeated for ADVM-043 related AEs of interest, Serious AEs of interest, ADVM-043 related serious AEs.

Listings for ADVM-043 related AEs of interest, serious AEs of interest will be listed similar to Listing 16.2.7.1 with respective information.

Death due to AEs will also be listed separately.

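### Planned death outputs draw only on AE records, so a known death judged unrelated and without an AE of interest adds zero to them

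*SAP*

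**What the plan says.** **Collection.** Protocol 6.2 states: "Only AEs of interest should be collected and reported". The four categories are new malignancy, neurologic disorder, rheumatologic or other autoimmune disorder, and "unexpected hospitalization". Death is not a category of its own. Protocol 6.3 names death as a criterion for seriousness but ends: "Only SAEs related to ADVM-043 should be collected and reported". SAP 10.6 repeats the AE restriction: "Only AEs of interest will be collected and reported in the current study".

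**Reporting.** The overall table in SAP 11.7.1.1 has six rows; the sixth is "Fatal adverse events". SAP 11.7.1.2 adds: "Death due to AEs will also be listed separately". SAP 11.7 sets the scope of the summaries: "Only AEs of interest will be summarized".

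**What the site records about a death.** Protocol 4.3 lists death first among the withdrawal circumstances and requires the withdrawal reason on the CRF. Protocol 6.10 covers any death during participation, whatever its presumed cause: "the Investigator should request a full autopsy to determine the precise cause of death". It also asks, where possible, for tissue to be tested for the AAV genome.

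**Disposition and listings.** SAP 11.1 summarizes early discontinuations by cohort with eight listed reasons, none of which is death, and lists disposition by subject. SAP 8 plans listings of all eCRF data.

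**The concern.** Long-term safety is the study's only objective, and its stated reason is that harm from the vector or from persistent transgene activity may be delayed by months or years. Whether a late death is related may be unclear when it happens, and the autopsy request is a way of finding out. A count of deaths from any cause needs neither a causality opinion nor a list of event types. The plan gives no such count. Every death figure in the safety section first passes through the AE-of-interest list or the investigator's judgement of relatedness.

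At stake is how the safety summary reads. A reader who sees zero in the only death row of the overall AE table, and an empty listing of deaths due to AEs, may conclude that nobody died. The contrary information would sit in the disposition section or a subject listing, possibly under a reason that does not say death.

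**Working it through.** The plan gives no death rate, sample size or mortality figure to reproduce. The check follows a death through the collection rules and then through the outputs.

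| Death known to the site | AE record created? | Fatal row (SAP 11.7.1.1) | Listing of deaths due to AEs (SAP 11.7.1.2) | Deaths from any cause (not planned) |
|---|---|---|---|---|
| (a) Due to an AE of interest, e.g. a new malignancy or an event leading to unexpected hospitalization | Yes, Protocol 6.2 | 1 | 1 | 1 |
| (b) Related SAE outside the four categories | Yes, Protocol 6.3 | Probably 1, but unclear | Probably 1 | 1 |
| (c) Judged unrelated, no AE of interest, e.g. sudden death at home without hospitalization | No, under 6.2 and 6.3 | 0 | 0 | 1 |

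Case (b) is unclear because SAP 11.7 confines the summaries to AEs of interest, while row 5 of the SAP 11.7.1.1 table counts related SAEs.

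Case (c) is the gap. The severity table in SAP 11.7.1.3 does not close it: Protocol 6.4 ties grade 5 to an AE, so a death without an AE record has no grade. With one type (c) death and no other, the fatal row shows 0 and a count from the CRF withdrawal reason shows 1.

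**Where the type (c) death does appear.** The withdrawal reason is on the CRF (Protocol 4.3). The subject is counted as an early discontinuation in SAP 11.1, most likely under the category for other reasons, since death is not offered. The subject also appears in the disposition listing and the general eCRF listings (SAP 11.1 and 8).

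**Direction.** With correct records, each fatal AE of interest or fatal related SAE is a death. So the number of subjects in the fatal row cannot exceed the number of known deaths, and it falls below that number for each type (c) death.

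**Size.** SAP 4.2 gives no sample size and SAP 10.2 names three cohorts without numbers of subjects. One death is 100/n percentage points of a cohort of n. For an assumed n of 2 to 6:

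- n = 2: 100/2 = 50.0
- n = 3: 100/3 = 33.3
- n = 4: 100/4 = 25.0
- n = 5: 100/5 = 20.0
- n = 6: 100/6 = 16.7

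**The case against.** **The outputs match the endpoint.** The primary endpoint is limited to AEs of interest and related SAEs, and the tables follow it. All-cause mortality is not an endpoint. This stands: the point is an addition to the safety reporting, not a correction of a miscalculated analysis.

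**The death is not lost.** A reader might infer that the plan hides such a death altogether. The documents do not support that, given the disposition table and the listings. Row 6 is also headed as fatal adverse events, not deaths, so a zero there is not in itself a false statement. What remains is that no safety summary gives the number of deaths, and the disposition reasons do not name death.

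**A record might exist after all.** Protocol 6.5 says that relatedness does not decide what gets reported and that doubtful observations are to be reported. A site following 6.5 might record an unrelated death; a site following 6.3 would not. This softens the claim that no AE record is ever created, but it means that similar deaths could be handled differently between sites.

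**Not every death is known.** A reader might infer that the protocol captures all deaths. It does not. Subjects can be lost to follow-up (Protocol 4.3), assessments are yearly, the autopsy is only a request, and AAV testing depends on feasibility. The point covers known deaths only.

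**The case is narrow.** A death preceded by an unexpected hospitalization or another AE of interest has an AE record. That stands and limits how often the gap would matter. The plan gives no basis for a probability.

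**The table index is redacted.** A planned death output there cannot be excluded. The SAP text describes none.

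**Conclusion.** The point holds for a known death judged unrelated and without an AE of interest. Such a death adds zero to the fatal row and to the listing of deaths due to AEs, and is visible only through disposition and general listings. The plan as written could therefore show no fatal events in its safety summary after a subject has died. It does not follow that the death is concealed, or that the study learns of every death.

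The direction needs only correct records: the fatal row is at most the number of known deaths. The size, 17 to 50 percentage points per death in a cohort, rests on an assumed 2 to 6 subjects per cohort and would hold for any single event in groups that small. The conclusion also assumes that sites follow Protocol 6.3 rather than 6.5, and that the redacted index holds no separate death output. The change is worth making because long-term safety is the sole objective and the fact of death should already be on the CRF.

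**What to change.** - **SAP 11.7.1.1:** add a row for deaths from any cause, by cohort, taken from the CRF withdrawal reason. Relabel row 6 to say that it covers fatal AEs of interest and fatal related SAEs.
- **SAP 11.7:** amend the sentence restricting summaries to AEs of interest, so that it agrees with rows 5 and 6 and allows the new row.
- **SAP 11.1:** add death to the reasons for not completing the study.
- **SAP 11.7.1.2:** list all known deaths with date and days since ADVM-043, plus cause, relationship, autopsy status and AAV genome result where available.
- **Protocol 6.3 and 6.5:** reconcile the rule that collects only related SAEs with the statement that relationship does not govern reporting, so that known deaths from any cause are recorded consistently. Carry the same rule into Protocol 6.2 and SAP 10.6.

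**Cost.** One table row, one listing, a disposition category and a short protocol edit, which needs ethics and biosafety committee approval under Protocol 11.1. The count itself uses the withdrawal reason that Protocol 4.3 already requires. Cause, relationship, autopsy and AAV results are not shown to be on the CRF for a death outside 6.2 and 6.3, so a small CRF addition may be needed. The mortality figure may look less favourable, and it will still miss deaths among subjects lost to follow-up; a footnote should say so.

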5.1 Screening Assessment

The Screening Assessment should be completed on the same day as the End-of-Study Visit in the prior ADVM-043 treatment study, irrespective of whether the subject completes the prior treatment study.

The following evaluations are to be conducted at the Screening Assessment:

- Informed consent
- Review of inclusion/exclusion criteria (re-confirm prior to enrollment at the Year 1 assessment)

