7.2 Secondary Endpoints

Not applicable

8 Statistical Methods

All analyses will be done using SAS (version 9.4, [REDACTED]).

Safety endpoints will be analyzed in a descriptive manner. Continuous data will be reported using the following descriptive statistics:

1. Number of observations (n)
2. Mean and Standard deviation (SD)
3. Median
4. Minimum (min) and Maximum (max)

Minimum and maximum values will be reported in the units of collection with 3 decimals being maximum value; the mean will be presented with 1 decimal place more and the standard deviation 2 decimal places more than the units of collection. Categorical data will be presented using frequency (n = number of subjects; m = number of events) and percentage (%).

Listings will be provided for all data recorded in eCRF to study subject profiles. All listings will be sorted by cohort, subject ID, and date (if applicable). Unscheduled visit data will only be listed and not included in summaries.

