8.3 Multiplicity Adjustment

Since the study is descriptive in nature, no multiplicity adjustment is required.

9 Analysis Populations

The membership of the analysis populations will be reviewed and finalized during the database lock.

Enrolled set will consist of all subjects who were previously treated with ADVM-043 in any clinical study.

The Full Analysis Set (FAS) consists of all subjects with A1AT deficiency who were previously treated with ADVM-043 in any clinical study and met all the eligibility criteria.

10 Analysis Variables

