10.5 Study Duration

Study Duration (years) = ((Date of Last Visit – Date of Informed Consent) + 1)/365.25.

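### AE frequency is reported only as a percentage of a fixed FAS denominator, with no confidence interval and no link to each subject's follow-up time

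*SAP*

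**What the plan says.** The frequency of AEs of interest and of related serious AEs is part of the only endpoint (Protocol 2.2.1, SAP 7.1). The SAP sets out its analysis as follows.

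- **Statistics.** SAP 8: "Safety endpoints will be analyzed in a descriptive manner". For categorical data, "Categorical data will be presented using frequency (n = number of subjects; m = number of events) and percentage". No interval is listed.
- **AE tables.** SAP 11.7.1.1: "Number and percentage of subjects will be summarized by cohort for the following categories", followed by "Percentages will be based on FAS population". SAP 11.7.1 puts every AE summary on the FAS, and 11.7.1.2 does the same by system organ class and preferred term.
- **Denominator.** Under SAP 9 the FAS is the subjects with A1AT deficiency who "were previously treated with ADVM-043 in any clinical study and met all the eligibility criteria". No minimum follow-up is required. SAP 8.1 rules out imputation.
- **Follow-up time.** SAP 10.5: "Study Duration (years) = ((Date of Last Visit – Date of Informed Consent) + 1)/365.25". This is summarised by cohort under disposition (11.1), and attendance at each visit is tabulated in 11.2. Neither is used in an AE table.
- **Unequal follow-up is foreseen.** Subjects screen on the day of the parent study's last visit, "irrespective of whether the subject completes the prior treatment study" (Protocol 5.1). Protocol 4.3 provides for withdrawal and loss to follow-up, and SAP 10.3 defines an early termination visit.
- **Imported events.** SAP 10.6 brings in AEs of interest still ongoing from the parent study and assigns each AE to a period by its start date.

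SAP 4.2 gives no sample size. Neither document states a cohort size or an expected dropout rate.

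**The concern.** The study exists because harm from a gene therapy vector may appear late. Subjects who leave early have had the least time to show such harm. Under the planned tables, a subject with no contact after screening and a subject followed without an event to Year 3 both add one to the denominator and nothing to the numerator. The percentage accurately describes what was recorded, but it is not the risk over the planned follow-up unless everyone was followed.

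A second gap is precision. Results are given for three dose cohorts and a total. A cell showing 0 tells the reader little without the range of true risks it leaves open, and the planned tables do not give that range.

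A third is that new and carried-over events may be mixed. SAP 10.6 can tell them apart by period, but the overall table in 11.7.1.1 does not say that imported events are left out or shown on their own line.

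**Working it through.** The documents give no sample size, event rate, dropout rate or confidence level, so there is no figure of theirs to reproduce. The planned follow-up of 2 years comes from Protocol 3.2 and SAP 5. All other inputs below are assumptions, shown as ranges, with a 95% level throughout.

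**1. Effect of dropout on the percentage (new-onset events only).** Let p be the true 2-year risk, with a constant hazard λ = −ln(1 − p)/2. A share d leaves at 1 year for reasons unrelated to the event. The expected crude percentage is

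(1 − d)·p + d·(1 − e^(−λ)).

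For p = 20%, λ = 0.1116 and 1 − e^(−λ) = 0.1056. With d = 20%, the result is 0.8 × 0.20 + 0.2 × 0.1056 = 0.1811. The shortfall is (0.20 − 0.1811)/0.20 = 9.4% relative, or 1.9 percentage points.

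| Share leaving at 1 year | Crude % when true risk is 20% | Relative shortfall |
|---|---|---|
| 10% | 19.1% | 4.7% |
| 20% | 18.1% | 9.4% |
| 30% | 17.2% | 14.2% |
| 50% | 15.3% | 23.6% |

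At 20% dropout the shortfall is 9.7% for p = 10% and 9.1% for p = 30%, so it depends little on the risk assumed. If leavers contribute no follow-up at all, the relative shortfall equals d.

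**2. What a zero leaves open.** The exact (Clopper-Pearson) two-sided 95% upper limit for 0 of n is 1 − 0.025^(1/n). For n = 3 this is 1 − 0.292 = 70.8%.

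| n (assumed) | 95% upper limit for 0 events | Chance of 0 events if true risk is 10% | Chance of 0 events if true risk is 20% |
|---|---|---|---|
| 3 | 70.8% | 0.73 | 0.51 |
| 6 | 45.9% | 0.53 | 0.26 |
| 10 | 30.8% | 0.35 | 0.11 |
| 20 | 16.8% | 0.12 | 0.01 |
| 30 | 11.6% | 0.04 | 0.001 |

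The chance of seeing none is (1 − p)^n.

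**3. The same on a person-time scale.** With zero events the exact Poisson two-sided 95% upper limit is −ln(0.025)/PY = 3.689/PY. Six subjects followed for 2 years give 12 person-years and a limit of 30.7 per 100 person-years. If mean follow-up is 1.5 years, that is 9 person-years and a limit of 41.0. The crude table shows 0% in both cases.

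**4. Comparing the two effects.** In a cohort of 6, one subject is 16.7 percentage points, whereas the dropout shortfall at 20% dropout is 1.9 points. In small cohorts the missing interval is therefore the larger matter.

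**The case against.** The plan is openly descriptive: "Since the study is descriptive in nature, no multiplicity adjustment is required". It names no 2-year risk as its target and draws no conclusion from a zero count. Unequal follow-up is disclosed: 11.1 gives study duration and discontinuations with reasons, 11.2 gives attendance, and all AEs are listed with their durations. Assessments can be done by telephone, and two calls and a registered letter are required before a subject is declared lost, so heavy dropout is not a given. A reader with n can work out an exact interval.

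Much of this stands, and it rules out three stronger readings that a reader might infer.

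- *Dropout biases AE frequency low.* This holds for new-onset events under non-informative dropout. It cannot be said of the overall count, because imported ongoing AEs may raise it. Early entry from the parent study lengthens a subject's observation here, so it does not push the percentage down either.
- *Time since dosing is never reported.* Visits are defined by year after treatment, and 11.2 tabulates attendance at each. What is absent is a summary of individual time from dose to last contact.
- *A zero in a very small cohort is presented as evidence of safety.* Neither document gives cohort sizes, and the SAP makes no such claim.

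What does not stand is that a descriptive purpose makes intervals and rates unnecessary. Both are descriptive statistics and need no hypothesis or multiplicity adjustment. Separate tables of duration and attendance do not give a rate, and an interval that readers must compute for themselves is not reported.

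**Conclusion.** The point holds as a weakness in how part of the primary endpoint is reported. The SAP specifies n and % on a fixed denominator, foresees unequal follow-up, derives individual duration, and does not connect the two.

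For new-onset events the understatement is moderate: about 9% to 10% relative if 20% leave at 1 year of 2. That figure rests on an assumed dropout rate, a constant hazard and non-informative dropout. With no dropout it disappears. For the overall count the net direction is unknown while imported events are not separated.

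The lack of an interval does not depend on dropout or on cohorts being very small. Even 0 of 30 leaves risks up to 11.6% open, and 0 of 3 leaves risks up to 70.8% open. The change is worth making before database lock. It affects reporting only, not the conduct of the study.

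**What to change.** In the overall AE table (SAP 11.7.1.1), by cohort and for the total:

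1. Show new-onset AEs separately from AEs imported from the parent study. The period assignment in SAP 10.6 already distinguishes them. A subject with both appears on both lines.
2. Add exact Clopper-Pearson 95% confidence intervals to the percentages. These show precision but do not correct for short follow-up, which is the purpose of item 3.
3. Add the new-onset incidence rate: subjects with a first new-onset event divided by person-years from screening to first new-onset event, death or last contact, with an exact Poisson 95% interval. Starting at screening matches the window in which new events are captured. A subject with an imported AE stays at risk for a new one.
4. Add a summary of time from ADVM-043 dose to last contact, using the administration data listed under SAP 11.6.

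Intervals and rates are not needed for every system organ class and preferred term row in 11.7.1.2.

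The cost is SAP wording, one derived person-time variable and a few table columns. No new data are collected. The intervals will be wide if cohorts are small, which would be an accurate picture of the information available.
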